8.3.1.2. Definition of Serious Adverse Event

A SAE is defined as any untoward medical occurrence that at any dose:

- Results in death
- Is life threatening, NOTE: The term "life-threatening" in the definition of "serious" refers to an event in which the patient was at risk of death at the time of the event; it does not refer to an event which hypothetically might have caused death if it were more severe
- Requires inpatient hospitalization or prolongation of existing hospitalization
- Results in persistent or significant disability/incapacity, or

- Is a congenital anomaly/birth defect
- Is an important medical event

Medical and scientific judgement should be exercised in deciding whether expedited reporting is appropriate in other situations, such as important medical events that may not be immediately life-threatening or result in death or hospitalization but may jeopardize the patient or may require intervention to prevent one of the other outcomes listed in the definition above. These should also usually be considered serious. Examples of such events include invasive or malignant cancers; intensive treatment in an emergency room or at home for allergic bronchospasm; blood dyscrasias or convulsions that do not result in hospitalization; or development of drug dependency or drug abuse.

An adverse event would meet the criterion of “requires hospitalization,” if the event necessitated an admission to a health care facility (eg, overnight stay).

The following reasons for hospitalization are exempted from being reported:

- Hospitalization for cosmetic elective surgery, or social and/or convenience reasons.
- Hospitalization for pre-planned (ie, planned prior to signing informed consent) surgery or standard monitoring of a pre-existing disease or medical condition that did not worsen, eg, hospitalization for coronary angiography in a patient with stable angina pectoris.

However, complications that occur during an exempted hospitalization are AEs or SAEs (for example if a complication prolongs a pre-planned hospitalization).

8.3.1.3. Definition of Adverse Event of Special Interest

Adverse events of special interest (AESI) in the CY 5032 study are defined based on clinical and laboratory parameters.

Clinically significant elevated transaminases and/or (total and if available, direct) bilirubin and manifestations of liver toxicity (e.g., rash, abdominal pain, nausea and vomiting, fatigue, dark-colored urine, light-colored bowel movements, jaundice, loss of appetite, fever) including elevations that prompt study drug discontinuation, are considered adverse events of special interest and should be reported to Cytokinetics Drug Safety within 24 hours of awareness on an AESI Report Form.

Any of the following criteria should be reported as Liver-Related AESIs:

- Manifestations of liver toxicity
- ALT or AST $>8 \times$ ULN
- ALT or AST $>5 \times$ ULN but $<8 \times$ ULN for ≥ 2 weeks;
- ALT or AST $>5 \times$ ULN but $<8 \times$ ULN and unable to adhere to monitoring;
- ALT or AST $>3 \times$ ULN w/signs or symptoms consistent with hepatitis (ie, right upper quadrant pain /tenderness, fever, nausea, vomiting, jaundice)
- TBL $>3 \times$ ULN
- TBL $>2 \times$ ULN or INR >1.5 AND ALT or AST $>3 \times$ ULN AND no alternative cause is apparent

Manifestations of renal toxicity, including clinically significant decreases in $eGFR_{Cr}$ and $eGFR_{CysC}$ and increases of UPCr, are also considered adverse events of special interest and should be recorded on the appropriate CRF and reported to Cytokinetics Drug Safety within 24 hours of awareness on an AESI Report Form.

Any of the following criteria should be reported as Renal-Related AESIs:

- Manifestations of renal toxicity
- Both $eGFR_{Cr}$, $eGFR_{CysC} < 30.0$ ml/min/1.73m²
- $UPCr \geq 3$ mg protein/g creatinine (or ≥ 339 mg protein/mmol creatinine)

In addition, if reldsemtiv has been temporarily interrupted or permanently discontinued related to renal labs that don't meet the above criteria, this is also considered as Renal-Related AESIs.

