7.3. Renal Function Monitoring and Study Drug Management

Reldesemtiv will be held if:

- Both $eGFR_{Cr}$ and $eGFR_{CysC} < 30.0$ ml/min/1.73m² or
- urine protein creatinine ratio (UPCR) is ≥ 3 mg protein/mg creatinine (or ≥ 339 mg protein/mmol creatinine)

Reldesemtiv may be restarted at half the dose, or 1 tablet twice a day (150 mg BID) when:

- Both $eGFR_{Cr}$ and $eGFR_{CysC}$ is > 40.0 ml/min/1.73m² and
- UPCR is ≤ 1.5 mg protein/mg creatinine (or ≤ 170 mg protein/mmol creatinine)

Serum cystatin C, $eGFR_{CysC}$, serum creatinine, and $eGFR_{Cr}$ will be obtained. These renal related laboratory results will be reviewed by the local investigator and the study drug should be held or restarted in the event the above criteria are met.

Abnormal renal function tests meeting the above criteria will be repeated. The site investigator and medical monitor should discuss and agree that study drug can be resumed or alternatively permanently discontinued. Agreement by the patient, site investigator, and medical monitor must occur for study drug to be resumed at a reduced dose.

1. If reldesemtiv is re-initiated, it must be at the lower dose of 150 mg BID,
or
2. If the abnormal renal function test requiring interruption of reldesemtiv occurred during administration of 150 mg twice daily, reldesemtiv 150 mg twice daily may be resumed once the laboratory value in question has returned to the threshold specified in the

protocol for re-initiation of reldesemtiv; however, should the same abnormal renal function test requiring reldesemtiv interruption recur, the patient must be permanently discontinued from reldesemtiv.

To accomplish this, the medical monitor may direct the laboratory assessments (serum cystatin C, eGFR_{CysC}, serum creatinine, eGFR_{Cr}, and UPCR) to be repeated as often as twice a week until a final disposition is reached (ie, re-initiation of study drug at 150 mg BID or permanent discontinuation) is reached.

Criteria for permanent discontinuation of study drug due to potential renal toxicity

Study drug **must** be discontinued permanently if the patient requires hemodialysis.

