8.2.2. Summaries of Adverse Events of Special Interest

Adverse events of special interest (AESI) in the CY 5032 study are defined based on clinical and laboratory parameters. Results for AESI will be reviewed individually. No summary table will be provided.

Clinically significant elevated transaminases and/or (total and if available, direct) bilirubin and manifestations of liver toxicity (e.g., rash, abdominal pain, nausea and vomiting, fatigue, dark-colored urine, light-colored bowel movements, jaundice, loss of appetite, fever) including elevations that prompt study drug discontinuation are considered adverse events of special interest and should be reported to Cytokinetics Drug Safety within 24 hours of awareness on an AESI Report Form.

Any of the following criteria should be reported as Liver-Related AESIs:

- Manifestations of liver toxicity
- ALT or AST $>8 \times$ ULN
- ALT or AST $>5 \times$ ULN but $<8 \times$ ULN for ≥ 2 weeks
- ALT or AST $> 5 \times$ ULN but $<8 \times$ ULN and unable to adhere to monitoring
- ALT or AST $>3 \times$ ULN w/signs or symptoms consistent with hepatitis (i.e., right upper quadrant pain /tenderness, fever, nausea, vomiting, jaundice)
- TBL $>3 \times$ ULN
- TBL $>2 \times$ ULN or INR >1.5 AND ALT or AST $>3 \times$ ULN AND no alternative cause is apparent

Manifestations of renal toxicity, including clinically significant decreases in $eGFR_{Cr}$ and $eGFR_{CysC}$ and increases of UPCr, are also considered adverse events of special interest and should be recorded on the appropriate CRF and reported to Cytokinetics Drug Safety within 24 hours of awareness on an AESI Report Form.

Any of the following criteria should be reported as Renal-Related AESIs:

- Manifestations of renal toxicity
- Both $eGFR_{Cr}$, $eGFR_{CysC} < 30.0$ ml/min/1.73m²

- UPCR \geq 3 mg protein/g creatinine (or \geq 339 mg protein/mmol creatinine)

In addition, if reldsemtiv has been temporarily interrupted or permanently discontinued related to renal labs that don't meet the above criteria, this is also considered as Renal-Related AESIs. Study drug dose management with the potential for a dosing interruption and down-titration of dose will be applied.

8.3. Total Duration of Therapy, Average Daily Dose, Maximum Daily Dose, Final Daily Dose of Study Medication, and Compliance

Total duration of treatment and exposure of study drug per day will be summarized overall.

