9. CHANGES TO PROTOCOL-SPECIFIED ANALYSES

As the study is prematurely stopped by Sponsor's decision, no formal statistical analysis will be produced. Only disposition, demographic and baseline characteristics, an overview of AEs and abnormal liver lab results will be summarized by table. By-subjects data listing will be produced for those with liver abnormality.

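### The renal AESI limit for urine protein creatinine ratio in Protocol 8.3.1.3 and SAP 8.2.2 is given in mg/g where mg/mg is meant, a 1000-fold unit error

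*Protocol*

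**What the plan says.** Protocol 8.3.1.3 lists the renal criteria under the words "Any of the following criteria should be reported as Renal-Related AESIs". One bullet is a UPCR of at least 3, in units given as "mg protein/g creatinine (or ≥ 339 mg protein/mmol creatinine". SAP 8.2.2 restates the list with the same unit: "3 mg protein/g creatinine".

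Protocol 7.3 uses the same laboratory measure for dosing. Drug is held when "urine protein creatinine ratio (UPCR) is ≥ 3 mg protein/mg creatinine", with 339 mg/mmol as the alternative unit. For restart, the UPCR condition is "UPCR is ≤ 1.5 mg protein/mg creatinine (or ≤ 170 mg protein/mmol creatinine".

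Two other routes to a renal AESI do not depend on the numeric UPCR limit. One is manifestations of renal toxicity, which include clinically significant UPCR increases. The other is a separate clause that applies "if reldsemtiv has been temporarily interrupted or permanently discontinued related to renal labs" when those labs fall short of the listed criteria.

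On use of the definition, SAP 8.2.2 says: "Results for AESI will be reviewed individually. No summary table will be provided". SAP 9 adds: "Only disposition, demographic and baseline characteristics, an overview of AEs and abnormal liver lab results will be summarized by table".

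**The concern.** The AESI bullet offers one limit in two units joined by 'or', and the two are not the same quantity. The number 3 and the figure 339 mg/mmol match the hold rule in Protocol 7.3, but the denominator has changed from mg to g of creatinine.

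The bullet is one of several stand-alone triggers. Renal AESIs go to the sponsor's drug safety group within 24 hours, and under Protocol 8.3.1.9 those still ongoing at the end of study are followed until resolution or stabilization. A reader who applied the mg/g figure would report UPCR values far below the intended limit, while a reader who applied the mg/mmol figure would not. The same patient could then be classified in two ways. The SAP carries the same wording into the section that governs the individual AESI review.

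**Working it through.** **Inputs, all from the documents**

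| Rule | Section | First unit | Second unit |
|---|---|---|---|
| Hold | Protocol 7.3 | 3 mg/mg | 339 mg/mmol |
| Restart | Protocol 7.3 | 1.5 mg/mg | 170 mg/mmol |
| Renal AESI | Protocol 8.3.1.3, SAP 8.2.2 | 3 mg/g | 339 mg/mmol |

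**Step 1. Conversion factor from the protocol's own pairs.** Factor = (mg/mmol) ÷ (mg/mg), in mg creatinine per mmol.
- Hold: 339 / 3 = 113.0
- Restart: 170 / 1.5 = 113.3

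These agree within rounding: 1.5 × 113 = 169.5, which rounds to 170. Both pairs in Protocol 7.3 therefore reproduce.

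**Step 2. The AESI pair as written.**
- 3 mg/g = 3 / 1000 = 0.003 mg/mg
- 0.003 × 113 = 0.339 mg/mmol
- 339 / 0.339 = 1000

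With the factor from the restart pair, 0.003 × 113.3 = 0.340 and 339 / 0.340 = 997. The AESI pair does not reproduce, and the gap is 997 to 1000 over the two factors. Against the hold threshold in the same unit it is exactly 3 / 0.003 = 1000.

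**Step 3. The AESI pair with mg/mg.** 3 × 113 = 339 mg/mmol, equal to 3000 mg/g. This reproduces the second figure on the AESI line and matches the hold threshold.

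**Step 4. Direction of the error.** The mg/g limit (0.003 mg/mg) lies below the intended limit (3 mg/mg). Every result at or above 3 mg/mg is also at or above 0.003 mg/mg, so no intended event is lost. The results wrongly brought in are those from 0.003 to below 3 mg/mg, that is 0.339 to below 339 mg/mmol.

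**Step 5. Plausibility.** The restart limit is 1.5 / 0.003 = 500 times the mg/g figure. This supports reading mg/g as a slip and shows no second error.

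**The case against.** The strongest reply is that this is a slip the documents largely resolve. The right value, 339 mg/mmol, stands on the same line and is just as literal as the mg/g figure. The same number with the right denominator is in the hold rule. The sentence that introduces the renal list speaks of clinically significant changes, and Protocol 8.3.1.1 says that laboratory findings without clinical significance are generally not recorded as adverse events. Mass reporting of trivial values is therefore unlikely. The study has also stopped early, and the SAP plans no AESI table.

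Most of this stands, and it is why the severity is low. It does not remove the error. The numeric bullet carries no clinical-significance condition of its own, and two incompatible limits joined by 'or' do not define one criterion.

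A reader might infer more than the documents support:
- **That the AESI and restart rules contradict each other.** They do not. A reporting trigger may lie below a dosing limit, and 8.3.1.3 itself makes interruptions for lesser renal abnormalities AESIs. AESI reporting does not control restart.
- **That events are missed, or that dosing or results change.** Step 4 rules out missed events, Protocol 7.3 is right in both units, and no table listed in SAP 9 uses the limit.
- **That sites have classified differently or over-reported.** Central laboratory testing is the default (Protocol Appendix 2), the UPCR reporting unit is not stated, and no counts of results or reports are given.

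**Conclusion.** The point holds as a unit error of low severity. In both documents the first unit of the renal AESI limit for UPCR is wrong by a factor of 1000 and should be mg/mg. The conclusion rests on the two conversion pairs in Protocol 7.3 and needs no outside figure. That mg/mg was intended is an inference, but a firm one: it is the reading that reconciles the AESI line with its own mg/mmol figure and with the hold threshold. The same unit appears in both documents, so a text-extraction fault is unlikely.

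The consequence is confined to possible over-reporting and inconsistent AESI classification in the band from 0.003 to below 3 mg/mg. How many results fall there cannot be determined from the documents.

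**What to change.** 1. In SAP 8.2.2, change the first unit of the UPCR criterion from mg/g to mg/mg.
2. Tell sites and the sponsor's drug safety group of the same correction to Protocol 8.3.1.3, by note to file or in the next amendment if there is one. This keeps the protocol and the SAP in agreement.
3. In the individual AESI review, apply at least 3 mg/mg (at least 339 mg/mmol) to the numeric UPCR criterion only. Keep as AESIs any lower UPCR events that qualify as clinically significant manifestations of renal toxicity, or through the clause on interruption or discontinuation for renal labs. Using 3 mg/mg as the sole test could drop valid AESIs.
4. Note the correction in the abbreviated CSR.

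The cost is one unit in the SAP, a short note to sites and drug safety, and a sentence in the CSR. The classification check fits within the planned AESI review. Protocol 10.1.1 requires IRB/IEC approval for amendments, and no stand-alone amendment is proposed here.

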8.3.1.4. Severity of Adverse Events

The investigator must assess the severity for each AE and SAE reported during the trial.

Severity describes the intensity (severity) of a specific event and is different from seriousness, which is based on patient/event outcome or action criteria and serves as a guide to determine the regulatory reporting obligations. The severity should be assessed by assigning a Grade of 1, 2, 3, 4 or 5 according to the Common Terminology Criteria for Adverse Events (CTCAE), version 5.0, as defined below:

- Grade 1 (Mild): asymptomatic or mild symptoms; clinical or diagnostic observations only; intervention not indicated.
- Grade 2 (Moderate): minimal, local or noninvasive intervention indicated; limiting age-appropriate instrumental activities of daily living (ADL)*.
- Grade 3 (Severe): Severe or medically significant but not immediately life-threatening; hospitalization or prolongation of hospitalization indicated; disabling; limiting self-care ADL**.
- Grade 4 (Life-Threatening): Life-threatening consequences; urgent intervention is indicated
- Grade 5 (Fatal): Death related to AE

* Instrumental ADL refers to preparing meals, shopping for groceries or clothes, using the telephone, managing money, etc.

**Self-care ADL refers to bathing, dressing and undressing, feeding self, using the toilet, taking medications, and not bedridden.

If the severity of an AE worsens during IP administration, only the worst severity should be reported on the AE page. If the AE lessens in intensity, no change in the severity is required.

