1.3. Schedule of Activities

	Day 1 ¹	Week 4	Week 6	Week 8	Week 12	Week 16	Week 18	Week 20	Week 24	Week 28	Week 32	Week 36	Week 40	Week 44	Week 48	FU (or ED): Week 52*
In Clinic	X				X				X			X			X	X
Remote Visit		X	X	X		X	X	X		X	X		X	X		
Informed Consent ²	X															
Inclusion and Exclusion Criteria	X															
Demographics	X															
Physical Examination	X ²															X
Neurological Exam	X ²															X
Weight & BMI	X				X				X			X			X	X
Concomitant Med Review	X	X		X	X	X		X	X	X	X	X	X	X	X	X
Vital Signs	X				X				X			X			X	X
AE/SAE Evaluation	X	X		X	X	X		X	X	X	X	X	X	X	X	X
Clinical Safety Labs ³	X		X ⁴		X		X ⁴		X			X			X	X
Pregnancy test (WOCBP only)	X ⁵								X						X	
Study Drug Dosing	X	X		X	X	X		X	X	X	X	X	X	X	X	
ALSFRS-R	X	X		X	X	X		X	X	X	X	X	X	X	X	X
Hospitalizations	X	X		X	X	X		X	X	X	X	X	X	X	X	X
DME Use	X	X		X	X	X		X	X	X	X	X	X	X	X	X

ED=Early discontinuation; AE=adverse event; BMI=body mass index; SAE=serious adverse event; WOCBP=women of childbearing potential; ALSFRS-R=Amyotrophic Lateral Sclerosis Functional Rating Scale-Revised; DME=Durable Medical Equipment

*Drug dosing will not occur at the ED visit

1=Day 1 of CY 5032 may occur on the same day as the Week 48 Visit or the FU Visit of CY 5031 or as a separate Day 1 Visit unique to CY 5032 that occurs after the CY 5031 FU Visit. If Day 1 in CY 5032 occurs more than 6-weeks after completion of the FU Visit in CY 5031, the initial dose of study drug will not be taken by the patient until their safety lab results are available and the estimated Glomerular Filtration Rate (eGFR)_{CySC} ≥ 45 ml/min/1.73m² and eGFR_{Cr} ≥ 45 ml/min/1.73m², alanine aminotransferase (ALT)/aspartate aminotransferase (AST) <3 × upper limit of normal (ULN), and bilirubin is normal or if abnormal reported as non-clinically significant by the investigator.

2=Physical Exam and Neurological Exam: Day 1 exams are only required if the patient enrolls in the OLE on the same day as the Week 48 visit in CY 5031 or at a separate Day 1 Visit unique to CY 5032 that occurs after the CY 5031 FU Visit; however, if a patient enrolls in the OLE at the FU visit in CY 5031, these exams do not need to be repeated on Day 1 of the OLE.

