8.3. Adverse Events and Serious Adverse Events

8.3.1. Adverse Events

8.3.1.1. Definition of Adverse Event

An AE is defined as any untoward medical occurrence in a patient or clinical investigation patient administered a pharmaceutical product and which does not necessarily have a causal relationship with this treatment. An AE can therefore be any unfavorable and unintended sign (including an abnormal laboratory finding), symptom, or disease temporally associated with the use of study drug, whether or not related to study drug.

Adverse events include:

- Exacerbation of a chronic or intermittent pre-existing condition (a condition that occurred before the patient was exposed to reldesemtiv) including either an increase in frequency and/or intensity of the condition.
- New conditions detected or diagnosed after IP administration even though it may have been present before the start of the trial.
- Abnormal assessments, eg, change on physical examination, electrocardiogram (ECG) findings, if they represent a clinically significant finding that was not present at trial start or worsened during the course of the trial.
- Laboratory test abnormalities if they represent a clinically significant finding, symptomatic or not, which was not present at trial start or worsened during the course of the trial, require treatment, or led to dose reduction, interruption or permanent discontinuation of IP. In general, abnormal laboratory findings without clinical significance (based on the investigator's judgment) are not to be recorded as adverse events. Where applicable, clinical sequelae (not the laboratory abnormality) are to be recorded as the adverse event.
- Signs, symptoms, or the clinical sequelae of a suspected drug-drug interaction.
- Signs, symptoms, or the clinical sequelae of a suspected overdose of either study drug or a concomitant medication. Overdose per se will not be reported as an AE/SAE unless it is an intentional overdose taken with possible suicidal/self-harming intent. Such overdoses should be reported regardless of sequelae.

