8.3.1.7. Reporting of AEs

The investigator is responsible for ensuring that all adverse events observed by the investigator or reported by the patient that occur after starting the study drug through end of study are recorded in the AE CRF.

ALS is a progressive and uniformly fatal neurodegenerative disorder associated with relentlessly progressive loss of motor function, including appendicular, craniobulbar, and respiratory function due to the degeneration of the upper and lower motor neurons which control and innervate the voluntary skeletal muscles. The following conditions are anticipated to occur in the study population as signs/symptoms of ALS progression and do not need to be recorded as an AE unless they meet the criteria for an SAE, are felt to be related to the study drug, or they are occurring outside what is expected for the normal course of the disease ([Brown 2017](#)).

Table 4: Signs and Symptoms Commonly Associated with ALS

MedDRA Preferred Term ^a	MedDRA Preferred Term ^a
Dysarthria	Muscle spasticity
Dysphagia	Muscle contractions involuntary
Dyspnoea	Muscle spasms
Gait disturbance	Muscular weakness

^aMedDRA Version 23.0

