9.2.4.1. Adverse Events

A treatment-emergent adverse event (TEAE) is an AE with an onset after initiation of study drug dosing in CY 5032, or an AE present at initiation of study drug dosing that worsens in severity after initiation of study drug dosing. All AE terms will be coded using the Medical Dictionary for Regulatory Activities (MedDRA). Primary system organ class (SOC) and preferred term (PT) of the TEAEs will be tabulated by the early-start and delayed-start treatment groups. TEAEs will also be summarized by severity and relationship to study drug. AEs that led to early discontinuation from treatment or the trial and adverse events of special interest will be summarized. Listings will be presented for patients who discontinued due to TEAEs.

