8.2. Adverse Events

8.2.1. Summaries of Adverse Event Incidence Rates for All Subjects

Adverse events (AEs) will be coded by System Organ Class (SOC) and Preferred Term (PT) using the Medical Dictionary for Regulatory Activities (MedDRA) version 26.0.

Analyses of AEs will be performed for those events that are considered treatment emergent AEs (TEAEs), where treatment emergence is defined as any adverse events with an onset after initiation of study drug dosing in CY 5032, or an AE present at initiation of study drug dosing that worsens in severity after initiation of study drug dosing. If an AE had the onset in the preceding study CY 5031 and carry over to the open-label extension, it will not be considered as treatment emergent in CY 5032 data.

The following summaries of AEs and serious AEs (SAEs) will be presented by overall:

- TEAEs by SOC and PT
- TEAEs by PT
- TEAEs by SOC, PT and Severity (Grade 1-5)
- TEAEs related to study drug by SOC and PT

- TEAEs related to study drug by PT
- TESAEs by SOC and PT
- TESAEs by PT
- TESAEs related to study drug by PT
- TEAEs leading to drug discontinuation by PT
- TEAEs leading to death

AE summaries will be presented by descending order of PT in the overall column, and if applicable, SOC will be ordered first, with PT sorted within the SOC.

A patient will be counted only once within each SOC and PT. For the summary of AEs by severity, patients will be counted only once within each primary SOC/preferred term and will only be counted under the maximum severity.

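### The worsening limb of the TEAE definition cannot be reliably derived from the AE data the protocol specifies, and SAP 8.2.1 contradicts that limb for events carried over from CY 5031

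*Protocol*

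**What the plan says.** **TEAE rule.** Protocol 9.2.4.1 counts AEs with onset after the first CY 5032 dose, and also "an AE present at initiation of study drug dosing that worsens in severity after initiation of study drug dosing". SAP 8.2.1 repeats both limbs. Its next sentence says that if an AE began in CY 5031 and should "carry over to the open-label extension, it will not be considered as treatment emergent in CY 5032 data". That sentence makes no exception for an event that worsens.

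**Recording rule.** Protocol 8.3.1.4: "If the severity of an AE worsens during IP administration, only the worst severity should be reported on the AE page". For improvement it adds: "If the AE lessens in intensity, no change in the severity is required".

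**Collection window.** Protocol 8.3.1.7 makes the investigator responsible for AEs "that occur after starting the study drug through end of study are recorded in the AE CRF". The Schedule of Activities (Protocol 1.3) marks "AE/SAE Evaluation" on Day 1, but does not say whether a grade for an ongoing event is stored. It has no row for medical history or ongoing conditions.

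**Exacerbations.** Protocol 8.3.1.1 lists exacerbation of a pre-existing condition as an AE, and defines pre-existing as "a condition that occurred before the patient was exposed to reldesemtiv".

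**Use.** The primary endpoint is AE incidence (Protocol 9.2.2, SAP 2.2.1). SAP 8.2.1 analyses AEs only as TEAEs. SAP section 9 cuts the analysis back after early termination and does not mention a change to the TEAE rule.

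**The concern.** In an extension study, an event that began on drug in the parent trial and becomes more severe with continued dosing is one of the signals long-term follow-up should show. The TEAE definition is written to catch it, but the data rules do not clearly provide what the definition needs, and the SAP then appears to remove the same events.

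Two consequences follow. First, classification may depend on how a site files the event. A worsening entered as a new AE has an onset after first dose and is counted. A worsening entered by updating the old record keeps its CY 5031 onset and is excluded. Second, a recorded high grade may have been reached before OLE Day 1, so it need not reflect the extension period. Both bear on the patient counts in the SAP 8.1 overview (TEAEs, TEAEs by severity). They also bear on the by-SOC, PT and severity tables of SAP 8.2.1, if those are produced: section 9 limits AE tables to an overview.

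**Working it through.** The plan gives no figure to reproduce. The check sets the rules side by side and enumerates the possible cases.

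**1. What the worsening limb needs.** Three facts: the event is present at first CY 5032 dose; its grade then (b); a higher grade afterwards.

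**2. What the AE page gives.** One worst grade (W), undated (8.3.1.4). Neither document asks for b, for the date of a grade change, or for a new record when an event worsens.

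**3. Can W alone classify an event known to be present at first dose?** Take b from 1 to 4 and W from b to 5.

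- Possible pairs: 5 + 4 + 3 + 2 = 14.
- W = 1: 1 pair, cannot have worsened.
- W = 5: 4 pairs, must have worsened.
- W = 2, 3 or 4: 2 + 3 + 4 = 9 pairs, of which 3 have b = W (not worsened) and 6 have b < W. Without b these cannot be separated.

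So 1 + 4 = 5 of the 14 pairs are classifiable and 9 are not. These are counts of logical cases, not expected frequencies. Because a fall in grade need not be recorded, W may also have been reached before Day 1. In that case even b < W would not show worsening after first dose.

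**4. Does a linked CY 5031 record help?** SAP section 8 lets the safety baseline come from CY 5031 and lists AE among the safety assessments. Let M be the worst CY 5031 grade for the same event.

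- CY 5032 worst grade above M: worsening is shown, provided the CY 5031 record runs up to first dose and the CY 5032 grade covers only the time after it.
- CY 5032 worst grade equal to or below M: generally still open. If CY 5031 also kept only the worst grade (an assumption), an event that peaked at Grade 3, eased to Grade 1 by Day 1 and then rose to Grade 2 would look no worse.

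The SAP does not say how AE records in the two studies are to be linked.

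**5. What the carry-over sentence does.** Read as written, onset date alone decides for CY 5031-onset events, so their first-dose grade no longer affects any planned TEAE count. The worsening limb is left chiefly with AEs that arise after CY 5031 but before a later Day 1. Protocol 1.3 allows that interval to exceed 6 weeks after the CY 5031 follow-up visit. Such events precede CY 5032 dosing, so 8.3.1.7 does not clearly collect them.

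**6. Does the exacerbation bullet rescue it?** Protocol 2.3.1 says every patient will have had at least 24 weeks of reldesemtiv before enrolling. A symptom that began on drug in CY 5031 therefore falls outside that bullet. Other bullets in 8.3.1.1 do reach clinically significant assessment and laboratory findings that worsen during the trial.

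**The case against.** The strongest reply is that the carry-over sentence settles the matter: if CY 5031-onset events are never treatment emergent, no first-dose grade is needed for them. That stands as a description of the sentence's effect. A reader might infer that the data gap matters equally under either TEAE rule. It does not: it affects the TEAE counts for these events only if worsening is kept. But the sentence then removes most of a limb that the protocol, and the sentence before it, put in place. One could read it as meant only for events that do not worsen, but it does not say so.

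Second, the lack of a first-dose grade is inferred from silence. The eCRF and its completion guide are not among the documents, and an AE evaluation is scheduled on Day 1. This stands as a limit. What can be said is that neither document requires the grade.

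Third, a reader might infer that the worsening limb cannot be derived at all. The documents do not support that: worst grades 1 and 5 are classifiable, a linked CY 5031 grade settles some others, and some worsening may have been entered as a new event.

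Fourth, the general AE definition in 8.3.1.1 is broad, and its laboratory and assessment bullets reach the renal and hepatic findings the protocol singles out in 2.3.1.1. This stands, and narrows the gap mainly to symptomatic events.

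Fifth, the study has stopped, so changes to recording rules may come too late. This also stands, and shifts the weight to the SAP.

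**Conclusion.** The point holds in limited form. Under the stated rules, the worsening limb of the TEAE definition cannot be reliably derived. SAP 8.2.1 contradicts itself and Protocol 9.2.4.1 on carried-over events that worsen, and section 9 does not declare the departure.

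Its reach is one limb of the definition. A reader might infer that the primary endpoint as a whole is compromised. The documents do not support that: the endpoint is AE incidence, and events with onset after first dose are unaffected.

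No number of patients can be given. The documents report neither how many patients entered with an ongoing AE nor how many such events worsened. The figure of about 400 is anticipated enrolment, in a study that was then terminated early. The conclusion assumes that the eCRF guide contains no first-dose grade or new-record rule. If it does, the capture part falls away and the SAP contradiction remains.

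**What to change.** **SAP 8.2.1 (the main change).**

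- Limit the carry-over exclusion to AEs that do not worsen after the first CY 5032 dose.
- Identify worsening by comparing the CY 5032 grade with the linked CY 5031 grade for the same event and preferred term, and state how the records are linked.
- Report the number of events that cannot be classified.
- List AEs ongoing at OLE Day 1 with the grades from both studies.

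If the sponsor prefers to keep the full exclusion, declare it in SAP section 9 as a departure from Protocol 9.2.4.1.

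**Protocol and CRF guideline (only if data are still being collected).**

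- In 8.3.1.4, have an AE ongoing at the first CY 5032 dose keep its grade at that dose, and have any later rise in grade open a new AE record dated at the rise. The single worst-grade record can stay for events that start in the extension.
- In 8.3.1.1, move the reference point for a pre-existing condition from first reldesemtiv exposure to the first dose in CY 5032.

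**Cost.** The SAP part takes one extra derivation using the CY 5031 AE data, one count and one listing. The protocol part means a few extra AE records for sites and an amendment, which needs IRB/IEC approval under Protocol 10.1.1. If collection has closed, only the SAP part applies.
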